#### **6.1.6. Pooling of Study Sites**

This is a study conducted at multiple study sites. Every effort will be made to have each site enroll at least 8 “index” subjects per arm. In case there are “small” sites each with fewer-than-8 “index” subjects per arm, these sites will be pooled together as a single, combined site for efficacy analyses if the combined site has at least 8 “index” subjects per arm. In the situation when the combined site still has less than 8 “index” subjects per arm, the smallest site with at least 8 “index” subjects per arm will be pooled to this combined site for efficacy analyses. Assessment of site-to-site variability will be conducted on the original sites prior to pooling.

## **6.2. Subject Characteristics**

### **6.2.1. Subject Disposition and Deviations**

The tabulation of number of subjects in each treatment group and overall will be displayed for all subjects who are screened, randomized, and in each analysis population.

The number and percent of subjects who completed or discontinued the study will be displayed for each treatment group and overall together with reasons for early termination, where the percent is with respect to the total number of randomized subjects in that treatment group.

Protocol deviations will be listed.

### **6.2.2. Treatment Compliance**

The compliance data will be listed for each subject. Compliance data consist of two parts: 1. Subject questioning about the application and removal of Investigational Product, and 2. Evaluate by investigator as to whether or not the Investigational Product was applied as instructed.

### **6.2.3. Demographic and other Baseline Characteristics**

Parameters collected at the screening and/or baseline visits will be summarized descriptively. In addition to the safety and efficacy scores listed in Sections 3 and 4, the following demographic and baseline characteristics will be presented:

- Demographic Characteristics
  - Sex (male, female)
  - Age (years)
  - Ethnicity and Race (Hispanic or Latino, American Indian or Alaska Native, Asian, Black or African American, Native Hawaiian or Other Pacific Islander, or White)
  - Baseline assessments of scabies infestation
  - Previous infestations

In addition, the above demographic and baseline characteristics will be presented by site before and after pooling the sites.

## **6.3. Efficacy Analysis**

### **6.3.1. Primary Efficacy Analysis**

The primary efficacy endpoint is the proportion of index subjects completely cured of scabies by Day 28. Complete cure is defined as demonstration of clinical cure (all signs

and symptoms have completely resolved, including burrows, inflammatory/non-inflammatory lesions and pruritus) and microscopic or dermatoscopic cure with demonstration of the absence of mites, eggs, and/or scybala, and dermatoscopy negative for burrows.

The primary analysis will be based on the data from the I-ITT population. The proportion of index subjects who exhibit complete cure (Yes or No) at Day 28 will be estimated by treatment group. Natroba™ will be compared versus placebo, and the difference with 2-sided 95% confidence interval (CI) will be provided. A Cochran-Mantel-Haenszel (CMH) general association test adjusted by study site (small sites pooled) stratification will be performed to test at an alpha level of 0.05 for equivalence in the complete cure rates between the two treatment groups.

Sensitivity analyses will be performed on the primary efficacy endpoint to evaluate the robustness of the results using different methods of analysis and other populations.

The similar CMH test will be performed based on observed cases (OC) data, LOCF, and imputed data from MI method as sensitivity analyses.

A logistic regression analysis will be used assessing the treatment group difference in complete cure rate by Day 28. The model will include clinical site (or region?) and treatment group as factors, and possibly additional baseline characteristics or a covariate, only if appropriate. The odds ratio, 95% CIs and p-value for the comparison will be provided. For logistic regression modelling, the data imputation approach specified in Section 6.1.5 for primary analysis will be applied for missing values at Day 28.

The similar logistic regression will also be performed based on observed cases (OC) data, LOCF and imputed data from MI method as sensitivity analyses.

The complete cure rates at Day 28 will be summarized descriptively by treatment groups and by sites before and after pooling the sites.

Other additional sensitivity analyses include repeating the above two statistical analyses on I-PP population and ITT population.

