### **3.2 Discussion of Study Design**

The phase 3 study design is a generally accepted clinical approach to provide sufficient pivotal results for the evaluation of safety and efficacy. The design for this trial is similar to the phase 3 trials evaluating efficacy of Natroba™ Topical Suspension for treatment of head lice except that in this study the subjects will receive only one application of Natroba™ Topical Suspension. In the two phase 3 studies of individuals with lice, all subjects who were treated on Day 0 returned for efficacy evaluation at Day 7. Subjects with live lice present at Day 7 received a second treatment. Subjects who were lice free on Day 7 were to return on Day 14 for evaluation. Subjects with live lice and who received a second treatment on Day 7 were to return on Days 14 and 21 for evaluation. Efficacy was assessed as the proportion of primary subjects who were free of live lice 14 days after the initial and/or final treatment.

The primary efficacy endpoint will be the proportion of “index” subjects completely cured of scabies by Day 28 after a single application of IP on Day 1. In households where efficacy results are likely to be correlated, selecting one subject (“index” subject) from each unit provides for efficacy results that are more independent. These subjects are selected according to a consistent criterion; in this study “index” subjects will be defined as the youngest ( $\geq 4$  years) infested member of the household. Thus the primary analysis population will be the “index” intent-to-treat (I-ITT) population which is defined as all randomized “index” subjects regardless of whether they have had any post-baseline assessments and the primary efficacy endpoint will be the proportion of “index” subjects completely cured of scabies by Day 28.

A large open-label, randomized, comparative, parallel clinical trial conducted in 315 patients with uncomplicated scabies assessed the efficacy and safety of topical Permethrin, oral ivermectin, and topical ivermectin. The first group received Permethrin 5% cream as single application, second group received tablet ivermectin 200 mcg/kg as single dose, and third group received ivermectin 1% lotion as single application. All the patients received anti-histaminic for pruritus. The patients were followed up at intervals of 1, 2, 3, and 4 weeks. Primary efficacy variable was clinical cure of lesions. Statistical analysis was done by chi square test and one-way

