## **6.8 Subject Completion Criteria**

Successful completion of the study by “index” subjects will occur at Day 28 (Visit 3) if the “index” subject is completely cured of scabies. Other household members will complete the study at Day 28 after safety assessments are completed.

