### **8.5.3 Efficacy Analyses**

#### **8.5.3.1 Primary Efficacy**

The primary efficacy endpoint is the proportion of index subjects completely cured of scabies by Day 28. Complete cure is defined as demonstration of clinical cure (all signs and symptoms have completely resolved, including burrows, inflammatory/non-inflammatory lesions and pruritus) and microscopic or dermatoscopic cure with demonstration of the absence of mites, eggs, and/or scybala, and dermatoscopy negative for burrows.

The primary analysis will be based on the data by Day 28 from the I-ITT population. The number and percentage of index subjects who exhibit complete cure (Yes or No) at Day 28 will be summarized by treatment group. A Cochran-Mantel-Haenszel general association test adjusted by study site (small sites pooled) stratification will be performed to compare the complete cure rates between the two treatment groups.

Sensitivity analyses will be performed on the primary efficacy endpoint to evaluate the robustness of the results using different methods of analysis.

A logistic regression analysis will be used assessing the treatment group differences. The model will include clinical site and treatment group as factors, and possibly additional baseline characteristics or a covariate, if appropriate.

Other additional sensitivity analyses include repeating the above analyses on I-PP population and ITT population.

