### **2.3.3. Method of Treatment Assignment and Randomization**

As “index” subjects and other infested or non-infested household members become eligible for randomization at Visit 1 (Day 1), the site will locally assign a unique subject number to each of the qualified household members that combines a 3-digit site number (xxx), a 2-digit household number (yy), and a 2-digit household member number (zz). For example, the first subject of the first household at site 101 would be randomized to subject number 101-01-01, the second member to 101-01-02, the third member to 101-01-03, and so on. Since all household members receive the same treatment, each household is randomized to either Natroba™ (spinosad) or Placebo control. Non-infested household members will be assigned the same IP treatment as the infested members and will be assigned a subject number and randomization number. The assigned subject numbers to each household will correspond to unique bottle numbers on a scheme that unblinded site personnel will assign and distribute, to ensure approximately equal randomization of households to either treatment. Subject numbers must not be re-used once assigned, even if the subject does not take the IP. Randomization will be stratified by study site.

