**6.1.5. Data Imputation Specifications**

For the safety analyses, no imputation of missing events or assessments are allowed.

For the primary efficacy endpoint (complete cure rate at Day 28), the algorithms listed below will be followed.

Any informative missing will be counted in as non-responders (failures) in the estimation of the treatment complete cure rates. Any non-informative missing will be imputed using Last Observation Carried Forward (LOCF) in the estimation of the treatment complete cure rates.

Table 2 Informative or Non-Informative Missing

Dropouts Due to			
Lack of Efficacy	Drug Related Adverse Event	Lost to Follow-up	All Other
Informative	Informative	Non-informative	Non-informative

For sensitivity analyses regarding the primary endpoint, the Observed Cases (OC), LOCF, and multiple imputation (MI) method will be used as appropriate approaches in addition to the imputation approach described for the primary efficacy analysis above. In addition, the Observed Case (OC) and LOCF methods will be used as sensitivity analyses for exploratory endpoints. Section 6.3 specifies in detail about imputation methods applicable to them.

The MI method assumes data are missing at random (MAR). The seed number is 626. The number of imputations is 5.

Step 1: Non-monotone missing data will be imputed using the fully conditional specification (FCS) method separately for each treatment arm since the response missingness could be due to treatment. A logistic regression will be used for binary data, and a discriminant function method will be used for ordinal data or classification variable with more than two levels if necessary. The following covariates will be included in the imputation model: treatment, clinical site (small sites pooled), baseline evidence of burrows and baseline score of lesions. In this step, MI procedure with FCS statement will be performed using SAS version 9.4.

Step 2: The combined imputed data sets will be analyzed using a Cochran-Mantel-Haenszel test and a logistic regression.

Step 3: The results from the analysis based on the multiply-imputed datasets will be combined by the MIANALYZE procedure in the SAS version 9.4. The p-value, estimate of odds ratio (Natroba™ vs Placebo), and the 95% confidence interval of odds ratio estimate from each multiply-imputed data set will be combined (Wilson & Hilferty, 1931; Gorja, 1992; Rubin, 1987; Li et al., 1991).

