#### Subset in ITT - subjects who were infested at baseline

A subset of subjects in ITT population who were infested at baseline will be summarized to display the proportion of the completely cured subjects.

The same analyses described for primary analysis will be performed for this subset of subjects using the similar data imputation approach described for primary analysis.

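### The complete-cure analyses that include several members per household (the ITT repeat and the infested-at-baseline subset) take no account of household, the unit that was randomised

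*SAP*

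**What the plan says.** Treatment is allocated by household. SAP 2.3.3: "Since all household members receive the same treatment, each household is randomized to either" arm. Protocol 3.2 explains why the primary analysis uses a single index subject: "In households where efficacy results are likely to be correlated, selecting one subject" from each unit makes the results more independent.

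The primary analysis (SAP 6.3.1) is a Cochran-Mantel-Haenszel (CMH) test stratified by pooled site in the I-ITT population, and "the difference with 2-sided 95% confidence interval (CI) will be provided". A logistic model with site and treatment follows as a sensitivity analysis, with baseline covariates optional.

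Two further analyses bring in several members of the same household:

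- **ITT repeat.** SAP 6.3.1: "Other additional sensitivity analyses include repeating the above two statistical analyses on I-PP population and ITT population". Protocol 8.5.3.1 agrees: "Other additional sensitivity analyses include repeating the above analyses on I-PP population and ITT population". SAP 5.2 defines ITT as all randomised subjects, both index subjects and enrolled household members.
- **Infested-at-baseline subset.** SAP 6.3.2: "The same analyses described for primary analysis will be performed for this subset of subjects". Protocol 8.5.3.2 leaves the detail of this subset to the SAP.

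Neither document specifies a household random effect, generalised estimating equations (GEE), a cluster-robust variance or a cluster-adjusted CMH test for either analysis.

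**The concern.** The plan recognises dependence within households and guards against it in the primary analysis by taking one subject from each. It then applies the same independent-observations methods to sets where that guard is gone. All members of a household share one arm, so positive correlation inflates the variance of the treatment comparison, and neither site stratification nor a baseline covariate corrects that variance.

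The ITT repeat is there to show that the primary result is robust. If its interval is too narrow and its p-value too small, it makes the primary result look better supported than it is. The same holds for the infested subset, which is likely to be read as evidence on treating whole households.

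**Working it through.** **1. The plan's own figure.** SAP 2.3.2 gives 80.0% power for 48 completed index subjects per arm at 60% v 30%, two-sided 0.05, Fisher exact test. Full enumeration gives 80.05%. The other two rows also reproduce (69 per arm: 80.40%; 37 per arm: 80.64%), as does the allowance for dropout: 96/(1 − 0.2) = 120. This calculation has one subject per household, so clustering does not enter it.

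**2. Inputs for the affected analyses.**
- Households: 120 (SAP 2.3.2).
- Mean household size: 360/120 = 3 (Protocol synopsis, Population).
- Test level: two-sided 0.05 (Protocol 8.5).
- Assumed, because the documents give no value: ICC 0.1, 0.3 or 0.6 within household (given site); probability u = 0.25, 0.5 or 0.75 that a non-index member is uninfested.

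**3. Formulae.** A household contributes m = 1 + Bin(2, 1 − u) infested members. Then:
- design effect DE = 1 + (E[m²]/E[m] − 1) × ICC
- true error of the nominal 5% test = 2 × (1 − Φ(1.96/√DE))
- ratio of correct to reported interval width = √DE

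Worked case, u = 0.25: E[m] = 2.5 and E[m²] = 2.5² + 2 × 0.75 × 0.25 = 6.625, so E[m²]/E[m] = 2.65. At ICC 0.6, DE = 1 + 1.65 × 0.6 = 1.990, the true error is 16.5% and the width ratio is 1.41.

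| u | ICC | DE | True error | Width ratio |
|---|---|---|---|---|
| 0.25 | 0.1 / 0.3 / 0.6 | 1.165 / 1.495 / 1.990 | 6.9 / 10.9 / 16.5% | 1.08 / 1.22 / 1.41 |
| 0.50 | 0.1 / 0.3 / 0.6 | 1.125 / 1.375 / 1.750 | 6.5 / 9.5 / 13.8% | 1.06 / 1.17 / 1.32 |
| 0.75 | 0.1 / 0.3 / 0.6 | 1.075 / 1.225 / 1.450 | 5.9 / 7.7 / 10.4% | 1.04 / 1.11 / 1.20 |

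**4. Simulation of the same nine settings** (infested members only; 120 households of 3, 6 sites, beta-binomial outcomes, no attrition, 1,500 runs each).

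| Quantity | Unclustered | Household-clustered |
|---|---|---|
| Null, 30% in both arms: test rejects | 5.5–17.8% (CMH) | 3.7–4.9% (GEE logistic, small-sample-corrected SE) |
| Null: 95% CI for the difference misses | 6.0–18.1% | 4.2–5.3% (identity-link GEE) |
| 60% v 30%: test rejects | 96.9–99.9% | 94.3–99.8% |

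The largest loss of power in any one setting is 3.4 points (99.5% to 96.1%). Clustered intervals average 1.08 to 1.44 times as wide, including the small-sample correction.

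**5. Variation.** If all three members had an outcome, DE = 1 + 2 × ICC. At ICC 0.1, 0.3 and 0.5 this gives 1.2, 1.6 and 2.0, with true error 7.4, 12.1 and 16.6%. A separate simulation of this case (20,000 runs per setting) gave 7.2, 12.5 and 17.1%. With sizes varying from 1 to 6 around a mean of 3, it gave 7.7, 13.8 and 18.7%, so unequal household sizes make the problem somewhat worse.

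**The case against.** The strongest reply is that little depends on these results. The plan deals with household correlation where it makes its claim, and one affected analysis is a sensitivity repeat and the other exploratory. At the plan's 60% v 30%, the clustered and unclustered tests would nearly always agree, and at ICC 0.1 the inflation is slight. All of that stands, and it limits the point to supportive results. It does not make the reported intervals correct: the direction of the error is certain for any positive correlation, which the protocol itself expects.

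A reader might infer more than the documents support:

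- **That the primary test or sample size is compromised.** It is not. I-ITT has one subject per household and I-PP is a subset of it.
- **That inflation could be far larger because households may have up to 6 members.** Six is an eligibility limit. If every household had 6, the trial would have 120 × 6 = 720 subjects, against 360 planned.
- **That never-infested members will be counted as cured in the ITT repeat, or that they plainly have no outcome.** Neither is established. Protocol 3.1 and SAP 2.2 tie complete cure to the index subject and any infested household members, without saying infested when. Protocol 3.1 also brings all members back for efficacy assessment, and the efficacy row of Table 6-1 has no restriction. Protocol 6.8 does not decide it: "Other household members will complete the study at Day 28 after safety assessments are completed" separates index from other members, not infested from uninfested.
- **That the multiple-imputation model is wrong for lacking a household term.** SAP 6.1.5 says "covariates will be included in the imputation model: treatment, clinical site (small sites pooled), baseline evidence of burrows" and a baseline lesion score. For a set with one subject per household that omission is no fault, and SAP 6.3.1 does not clearly carry multiple imputation over to the ITT set.

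**Conclusion.** The point holds for two supportive analyses. As written, the ITT repeat and the infested-at-baseline subset treat members of a randomised household as independent, so under positive within-household correlation they overstate precision. The size depends on an ICC and an infested share that the documents do not give. Under the assumptions above, true error runs from close to nominal (5.9%) to about three times nominal (16.5%). The 0.6 end of the ICC range is an assumption, not an estimate. The primary conclusion does not depend on these results. The correction is still worth making before unblinding, because it is cheap and the affected outputs will be cited as evidence of robustness.

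**What to change.** In SAP 6.3.1 and 6.3.2, state that any complete-cure analysis with more than one member per household uses household as the cluster. For example:

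- **Odds ratio, CI and p-value:** GEE logistic model with treatment and pooled site, exchangeable working correlation fixed in advance, and small-sample-corrected robust standard errors.
- **Risk difference and 95% CI:** a household-clustered standard error, such as the same GEE with identity link.
- **CMH:** a cluster-adjusted CMH may stand in, if a closer repeat of the planned test is wanted.
- **Multiple imputation, if applied to these sets:** run the clustered analysis in each imputed data set, then combine.

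Separately, state which ITT members have a complete-cure outcome in the ITT repeat. If only those infested at baseline count, the repeat and the subset are the same set and should be reported once. Leave the primary I-ITT analysis unchanged.

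**Cost.** A SAP revision and a few lines of code; household is already the middle block of the subject number (SAP 2.3.3). Intervals in these analyses become about 4 to 41% wider by formula under the stated assumptions, with a simulated power loss of at most about 3.4 points at 60% v 30%. FDA agreement may be needed (Protocol 8.5, SAP 1), since the ITT repeat is a sensitivity analysis of the primary endpoint. If Protocol 8.5.3.1 is edited as well, Protocol 12.1 requires an amendment and IRB submission.

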## 8.5 Statistical Analyses

A statistical analysis plan (SAP), in addition to this section of the study protocol, will describe statistical methodology for analyses and data reporting. A version of the SAP will be prepared at the same time as the protocol is finalized. However, the primary and secondary efficacy endpoints and analyses on them will not be altered unless agreed upon with the FDA. SAP will be finalized before the database is unblinded.

Data collected in this study will be presented using summary tables, figures, and subject data listings. Summary tables will present data by treatment group and, if applicable, by scheduled time of data collection. Continuous variables will be summarized using descriptive statistics, presenting the number of subjects, mean, standard deviation, median, minimum, and maximum. Categorical variables will be summarized by frequencies and percentages. Figures may be used to support the presentation of certain data.

For efficacy analyses, small study sites may be pooled together. Details on the pooling algorithms are provided in Section 8.5.3.3.

All statistical tests and confidence intervals will be 2-sided at an alpha level of 0.05.

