### 2.3.2. Sample Size Determination

Approximately 120 “index” subjects will be enrolled (includes anticipated 20% attrition) from 120 households and randomized 1:1 to Natroba™ (spinosad) and Placebo control. The index subject will be the youngest infested member of a household ( $\geq 4$  years). Referencing to the Sponsor’s Proof of Concept (POC) study (SPN-401-12) and published literature, it is reasonable to assume a 60% complete cure rate for Natroba™ and 30% for placebo. A sample size of 48 study-completed “index” subjects per group will provide 80% power to declare the non-equivalency using a delta of 30% and Type I error rate of 0.05. Fisher exact test was used to calculate the sample size and the specified power in the following Table 1 (PASS 14; 2015, NCCSS, LLC., Kaysville, Utah, USA. [www.ncss.com](http://www.ncss.com)).

**Table 1 Sample Size Needed to Declare Non-equivalency with Respect to the Proportion of Subjects Achieving Complete Cure with a Type I Error Rate=0.05 and Specified Power**

Natroba™	Proportion in		Required Sample Size per Group	Power
	Placebo	Difference vs. Placebo		
55%	30%	25%	69	80.4%
60%	30%	30%	48	80.0%
65%	30%	35%	37	80.6%

Assuming a drop-out rate could be at most 20%, 120 subjects should guarantee at least 48 evaluable subjects for each treatment group at Day 28 assessment.

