### **5.2. Intent-to-Treat Population**

The intent-to-treat (ITT) population will comprise all subjects who were randomized. Subjects will be analyzed as randomized. This population includes the index subjects along with any household members enrolled in the study.

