## **6. STATISTICAL METHODOLOGY**

### **6.1. Statistical and Analytical Issues**

#### **6.1.1. Statistical Methods**

This statistical analysis plan (SAP) will describe statistical analyses for the study and be completed at the same time as the protocol. Any revisions (both alternative and additional methods) to the SAP, and reasons for such revisions, will be described in the final clinical study report.

Data collected in this study will be presented using summary tables, figures, and subject data listings. Summary tables will present data by treatment group and, if applicable, by time of collection. Continuous variables will be summarized using descriptive statistics, specifically the number of non-missing observations, mean, median, standard deviation, minimum and maximum. Categorical variables will be summarized by frequencies and percentages. Figures may be used to support the presentation of certain data.

All tests of significance, unless otherwise stated, will be performed at a significance level of  $\alpha=0.05$ , two-sided.

Statistical programming and analyses will be performed using SAS® Software (SAS Institute Inc., Cary, NC) Version 9.2 or higher.

All subject study data, including data not appearing in tables or figures, will be presented in data listings.

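### The ITT repeat of the complete-cure analyses includes household members not infested at baseline, for whom cure is trivial or undefined, and the plan gives no rule for scoring them

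*SAP*

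**What the plan says.** **Who is randomised.** Protocol 5.3 and SAP 2.3.3 randomise by household and give uninfested members a subject number and a randomisation number. The protocol synopsis plans about two further members per household, infested or not, so that 240 of roughly 360 subjects are non-index (SAP 5.1).

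**Who is in the ITT.** All randomised subjects, with no condition on infestation (Protocol 8.3). SAP 5.2: "This population includes the index subjects along with any household members enrolled in the study".

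**What is repeated on it.** After describing the CMH test and the logistic regression of complete cure, SAP 6.3.1 says: "Other additional sensitivity analyses include repeating the above two statistical analyses on I-PP population and ITT population". Protocol 8.5.3.1 says the same: "Other additional sensitivity analyses include repeating the above analyses on I-PP population and ITT population".

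**The infested members are named separately.** SAP 6.3.2, under exploratory efficacy: "A subset of subjects in ITT population who were infested at baseline will be summarized". The primary analyses are then applied to that subset. Protocol 8.5.3.2 has the same subset.

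**Who is assessed for cure.** The synopsis, Protocol 3.1 and SAP 2.2 assess complete cure on Day 28 in the index subject and in infested household members. Protocol 6.8 lets other members complete once their safety assessments are done. In contrast, Protocol 3.1 brings all household members back for efficacy as well as safety assessments. Protocol 7.6, SAP 4.1 and the efficacy row of Table 6-1 do not limit the examination to infested subjects.

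**The concern.** The objective is complete cure after a single treatment, and a person without scabies on Day 1 cannot contribute to it. If such a member is examined and found clean on Day 28, the criteria are satisfied in either arm whatever the treatment did. If the member has acquired scabies by then, a failure of prevention would be recorded as a failure of cure.

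A sensitivity analysis is meant to show whether the primary result survives a change of method or population. This one changes the quantity being estimated. Agreement with the primary result would not show robustness, and disagreement would not show fragility. It would also put percentages labelled as cure into the report that are not cure rates. With no scoring rule, the choice falls to whoever programs the table, possibly after unblinding.

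This is separate from the correlation of outcomes within households.

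**Working it through.** **1. The plan's own figure.** SAP 2.3.2 assumes that "it is reasonable to assume a 60% complete cure rate for Natroba™ and 30% for placebo", and that 48 completed index subjects per group "will provide 80% power to declare the non-equivalency using a delta of 30% and Type I error rate of 0.05". Tests are two-sided: "All statistical tests and confidence intervals will be 2-sided at an alpha level of 0.05" (Protocol 8.5). Exact enumeration of the Fisher test over two binomials gives 80.05% power at 48 per group, against 80.0% stated. The other two rows of the table also reproduce: 80.4% at 69 per group and 80.6% at 37. Allowing for dropout, 96 / 0.80 = 120. All of this rests on index subjects, who are infested by definition.

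**2. Inputs for the ITT repeat.** Per arm there are 60 index and 120 non-index subjects, 180 in all (half of the planned 120 and 240). Let q be the share of non-index members uninfested at baseline. The documents do not give q, so a range is used. The uninfested share of the ITT is w = 120q / 180 = 2q / 3. Infested non-index members are assumed to cure at the index rates. Let a and c be the proportions of uninfested members found clean on Day 28 on active and placebo. Scoring them from that examination is also an assumption.

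- Active rate = 0.60(1 − w) + a·w
- Placebo rate = 0.30(1 − w) + c·w
- Difference = 0.30(1 − w) + w(a − c)

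**3. No new infestations (a = c = 1).**

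| q | w | Active | Placebo | Difference (points) | Odds ratio |
|---|---|---|---|---|---|
| 0 | 0 | 60.0% | 30.0% | 30.0 | 3.50 |
| 25% | 1/6 | 66.7% | 41.7% | 25.0 | 2.80 |
| 50% | 1/3 | 73.3% | 53.3% | 20.0 | 2.41 |
| 75% | 1/2 | 80.0% | 65.0% | 15.0 | 2.15 |
| 100% | 2/3 | 86.7% | 76.7% | 10.0 | 1.98 |

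Example at q = 50%: active 0.60 × 2/3 + 1/3 = 0.733; placebo 0.30 × 2/3 + 1/3 = 0.533; odds ratio (0.733 / 0.267) / (0.533 / 0.467) = 2.41.

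**4. New infestations on placebo only (a = 1, c = 0.8, assumed).**

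- q = 50%: placebo = 0.20 + 0.333 × 0.8 = 46.7%; difference 26.7 points; odds ratio 3.14. Of the 26.7 points, 0.333 × 0.20 = 6.7 are prevention and 20 are cure.
- q = 100%: placebo = 0.10 + 0.667 × 0.8 = 63.3% against 86.7% on active; difference 23.3 points; odds ratio 3.76. The difference is below 30 points while the odds ratio is above 3.50.
- By the difference formula, the 30 points are restored when a − c = 0.30. At q = 50%: 0.20 + 0.333 × 0.30 = 0.30.

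The direction of the distortion therefore depends on the uninfested share, on new infestations and on the scale used.

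**5. Ways an uninfested member could be handled under the present text.**

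- Examined on Day 28 and scored from the findings: trivially cured, or a failure if newly infested.
- Completed but not assessed for cure: Table 2 in SAP 6.1.5 classifies dropouts only, so no imputation category applies.
- Dropped out for a non-informative reason: LOCF applies, but the schedule places efficacy assessments only at Day 28 or early termination. No Day 1 complete-cure value is specified to carry forward.
- Left out as not assessable: the repeat then reduces to the infested subset of SAP 6.3.2.

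**The case against.** The strongest reply is that nowhere do the documents score uninfested members as cured. The Day 28 cure assessment is described for index subjects and infested members, others complete after safety assessments, and the definition speaks of signs and symptoms having resolved, which presupposes that they were present. On that reading these members have no complete-cure value and an observed-case repeat drops them. This stands as far as it goes: a reader might infer from the population definition that uninfested members will be counted as cured, and the documents do not establish that. But the passages that bring everyone back for efficacy assessment, and the unrestricted skin examination, leave the other reading open. Nothing in SAP 6.3.1 excludes anyone from the ITT repeat, and naming the infested subset elsewhere implies that the repeat is wider.

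Second, the infested-only analysis is already planned, with the primary methods and similar imputation, so a usable estimate will be in the report. That is correct and limits the harm. It does not repair the sensitivity analysis named for the primary endpoint, because the usable version is classed as exploratory.

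Third, the size is not known. The uninfested share is not in the documents, and the tabulated dilution assumes no new infestations, although uninfested members of placebo households live with someone receiving only vehicle. This also stands. A reader might conclude that the ITT repeat must understate the effect; the calculations do not support a fixed direction.

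**Conclusion.** The point holds for one sensitivity analysis. As written, the ITT repeat of the CMH and logistic analyses covers randomised members for whom complete cure is trivial or undefined, and no rule says how they are scored or excluded.

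If they are scored from a clean Day 28 examination, the planned 30-point difference becomes 25 to 15 points and the odds ratio 2.80 to 2.15. This rests on four assumptions: 25% to 75% of non-index members uninfested, infested non-index members curing at the index rates, that scoring rule, and no new infestations. With new infestations on placebo the estimate blends cure with prevention and can lie on either side of the cure effect.

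A reader might take this to mean that the trial's cure rates and treatment effect are wrong. The documents do not support that. The primary analysis uses index subjects only, all infested by definition; the index per-protocol population is a subset of them; the sample size is built on them and reproduces; and the plan makes no success criterion depend on the ITT repeat.

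**What to change.** - In SAP 6.3.1 and Protocol 8.5.3.1, replace *ITT population* in the sentence on additional sensitivity analyses with *ITT subjects infested at baseline*. Merge this with the exploratory subset analysis in SAP 6.3.2 and Protocol 8.5.3.2, so that it is run once and has one status.
- State that members not infested at baseline have no complete-cure outcome and enter no cure-rate denominator.
- Report the Day 28 scabies status of those members by arm in a separate table, where it was assessed.

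The cost is a few sentences, settled before unblinding, and no new data. One planned table is dropped or relabelled. Both documents tie changes to analyses of the primary endpoint to agreement with the FDA, so the sponsor should check whether this wording change needs it.
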